1.4 Study Design

This study is a double-blind, placebo-controlled, two-arm trial in which 120 binge drinkers with AUD will be randomly assigned to receive 12 weeks of kudzu or placebo, to be taken on an as-needed basis (see Figure 2) with 1- and 3-month post-treatment follow-up visits. This efficacy study will enroll sexually active, binge drinkers with AUD because they are the most likely population to benefit from this intervention by limiting harms associated with heavy alcohol use and decreasing alcohol-related sexual risk behaviors. A study clinician will perform the Structured Clinical Interview for the DSM-V (SCID) to screen for AUD and determine eligibility. Upon enrollment, 120 participants will be randomized 1:1 to kudzu extract (2 grams) or placebo for targeted administration. Participants will be seen weekly for behavioral surveys, urinalyses, study drug dispensing, and alcohol use counseling. Safety laboratory assessment, vital signs, and the audio computer assisted survey instrument (ACASI) will be completed monthly. Efficacy, tolerability, and acceptability (Specific Aims 1-4) will be assessed upon trial completion as measured by number of binge drinking occasions and numbers of drinks on drinking days via timeline follow-back at weekly visits; number of EtG-positive urine samples; sexual risk behavior data through monthly surveys via ACASI; frequency of adverse events; and cumulative medication adherence data at week 12. Durability of intervention effects will be evaluated at 1- and 3-month post-treatment visits.

1.4.a. Study Participants, recruitment, and inclusion/exclusion criteria. We will recruit a total of 120 racially/ethnically diverse sexually active, binge drinkers with AUD will be enrolled in the study. Subjects will be San Francisco Bay Area residents between 18-70 years of age. The project is designed specifically for binge-drinkers at high risk for HIV transmission or acquisition.

1.4.b. Recruitment.

For this study, we will combine several strategies that have proven successful in our previous studies with alcohol- and substance-using individuals:

Advertisements: We will run advertisements in the local papers catering to the community and widely read by our participants.

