Participants will be randomly assigned, sequentially as they qualify for the study, to either kudzu or placebo in a 1:1 ratio per a computer-generated list, stratified by gender, provided by a biostatistician. Randomization will be balanced using permuted blocks. Stratification by gender will ensure balance of treatment assignment within genders. Participants and investigators will be blinded to assignment.

1.5.e. Procedures for assignment to a study group, and medication dispensing.

Participants will be assigned to kudzu or placebo by a double-blinded block randomization procedure, stratified by gender. The stratified randomization code, which will have variable blocks and 1:1 randomization, will be provided by the statistician directly to the pharmacy. No study staff will have access to the code. Study medication (kudzu and placebo) will be prepared by pharmacists at Natural Pharmacie International (NPI) in identical, absorbable gelatin caps to maintain the double-blind. The study drug will be dispensed by the study clinicians in MEMs cap dispensers with dosing instructions, date of dispensing, prescribing clinician, a 24-hour telephone study phone number for medical emergencies, and advisements against drug combinations. Participants will be trained on targeted dosing of medication during enrollment and be provided a quick guide instructional leaflet for reference. Consistent with prior targeted dosing studies, participants will be instructed to take a single 2 gram dose when they believe that drinking is imminent or anticipate a drinking session.⁵⁶ For the proposed study, a single dose of the study drug will be comprised of four 500 mg capsules of kudzu extract (NPI-031, Natural Pharmacia International, Belmont, MA) or matching placebo, which is consistent with a recent human laboratory study that established the quick-acting, protective effect of a single dose of kudzu.⁸⁸ Participants will be given seven 2 gram doses (28 500 mg capsules) per week and will be instructed to not exceed a single dose (4 capsules) every 24 hours.⁵⁶ Participants will be briefed about the importance of not sharing medications.

1.5.f. Medical Management.

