AE Reporting. Each AE will be classified by the study clinician as serious or non-serious, and appropriate reporting procedures will be followed; these decisions will be reviewed on a real-time basis by the study clinicians. An AE is defined as any reaction, side effect, or untoward event that occurs during the course of the clinical trial, whether or not the event is considered medication-related. A new illness, symptom, or worsening of a pre-existing condition or abnormality is considered an AE. Stable chronic conditions that are present prior to clinical trial

entry and do not worsen are not considered AEs. For this study, AEs will include symptoms reported by the patient and abnormal measures of clinical importance noted by study staff.

Study staff will assess participants for any medical or psychiatric side effects by asking the participant "How have you been feeling since I saw you last?" Study staff will also review the previous AE form and inquire whether any of those events are continuing. Study clinicians will follow all AEs, regardless of severity, until resolution or until four weeks following completion of the trial. Each new or unresolved AE will be recorded on the AE case report form according to standard procedures. All AEs will be assigned a severity (mild, moderate, severe or life-threatening), as defined by the DAIDS Table for Grading Severity of Adult Adverse Experiences for HIV Prevention Trials. 148 The study clinician will review the information and offer an educated opinion about the relatedness of the event to the study drug. These data will be reviewed by the PI or Co-Investigator on a weekly basis.

A summary report of all AEs (including SAEs) will be prepared at least every six months (frequency determined by our IRB, DSMB, and NIH), to be submitted to the DSMB, IRB and NIH.

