Trial stopping rules: There are no formal trial stopping rules for this study. No formal interim efficacy analysis will be conducted. If it becomes clear that the trial puts undue safety risk on study participants, outcomes are poor, or the trial will not achieve its enrollment goals, consideration will be given to stopping the trial, after consultation with the DSMB, IRB, and NIDA PO. The overall safety risk to study participants will be determined through regular monitoring procedures. Safety issues will be evaluated as they arise; participants are given the pager number of the clinician on call which they can page in the event of an emergency or safety risk. Study clinicians will consult with [name], the Principal Investigator and [name], the medical director, on these safety issues on a case-by-case basis as they are reported by the participant. Non-urgent clinical issues that arise during the course of the study are discussed by the team's research clinicians at the next weekly meeting with the PI [name]. During weekly meetings, study clinicians will review all the safety issues and incident adverse events (including lab abnormalities) for the study overall, by system category, and by possible relationship to the study drug. The PI will alert the DSMB and the NIDA PO immediately if at any point the team observes an unexpected frequency of serious AEs possibly related to kudzu. At that point, the PI will consult with the DSMB to determine if changes to the protocol or consent form are needed, or if additional safety data are needed to evaluate participant safety. The PI will consult the DSMB to determine if the trial should be stopped after the committee has reviewed available safety data to date.

1.5.d. Measures of adherence.

The study will collect self-reported adherence data via weekly modified TLFB assessments, similar to prior targeted dosing studies^{94,98} and via daily SMS text messages. Pill counts at weekly visits will also assess adherence. **MEMs cap Dispensers**, as with our Project iN and Say When studies, will be used to track medication adherence daily; each dispenser opening is recorded as a medication event in a remote database in real time. MEMs cap Dispensers have been shown to be reliable for real time monitoring of medication adherence, even in resource-limited

settings.¹⁶⁹ We have had great success with electronic medical monitoring devices in prior studies.^{125,126}

1.1.e. Text messaging procedure.

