We will use generalized estimating equations (GEE) to estimate treatment effects on repeated study outcomes. Primary analyses will be by intention-to-treat, without regard to adherence to treatment. In our prior trials, we had excellent retention and visit adherence. Nonetheless, in this high risk population, missing data may be encountered.^{175,176} We will conduct sensitivity analyses imputing all missing urine samples as positive, adjusting for baseline correlates of missingness, and using inverse probability of censoring weights.¹⁷⁷

Aim 1: To determine the efficacy of targeted kudzu versus placebo in reducing binge drinking among sexually active binge drinkers with AUD, as determined by number of binge drinking days in timeline follow-back (TLFB), by treatment arm. GEE Poisson models with robust standard

errors will be used to assess reductions on weekly drinking outcomes. Baseline TLFB results will be included in the analysis. Minimum detectable effects (MDEs): Based on the prior Project iN trial (93% retention), we conservatively estimate that 80% of participants will be retained at 12 weeks. Using estimates based on Project ECHO for the within-subject correlation and over-dispersion of the outcomes, as well as the mean frequency among controls, we estimate that this study will have 80% power in 2-sided tests with a type-I error rate of 5% to detect 28% reductions in numbers of binge drinking occasions, as well as 11% reductions in the average number of drinks on drinking days. In exploratory analyses, we will evaluate the durability of intervention effects on drinking outcomes at 1- and 3-month post-treatment visits.

Aim 2: *To determine the efficacy of targeted kudzu versus placebo in reducing alcohol consumption among non-dependent individuals with AUD*, as determined by the proportion of ethyl glucuronide (EtG) positive urines, by treatment arm. GEE logistic models with robust standard errors will be used to assess reductions frequency of positive urine tests, accounting for within-subject correlation. MDEs: Using the assumptions for retention for Aim 1, as well as estimates based on biomarker data from [name] et al.'s study on topiramate for alcohol use disorders¹⁷⁴ for the within-subject correlation and control group urine positivity rate, we estimate that the study will have 80% power in 2-sided tests with a type-I error rate of 5% to detect 15-24% reductions in the urine positivity rate in the treatment arm.

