***Aim 4:** To evaluate the tolerability and acceptability of targeted kudzu versus placebo*, as determined by adverse clinical event rates and medication adherence (via data from MEMs capmonitoring and self-report from EMA and TLFB), by study arm. While laboratory studies have demonstrated the tolerability and acceptability of daily kudzu, we will examine these outcomes in an outpatient setting for targeted (prn) dosing. Adverse clinical events (AEs) and other binary safety outcomes will be presented as percent of participants that experience the safety outcome by treatment arm. Binary adverse effect measures will be analyzed using exact methods, since they are expected to be uncommon. We will measure the acceptability of kudzu among participants by determining medication adherence via MEMs cap opening events, pill count and self-report. Adherence measures of interest will include percent of doses taken during reported drinking days, patterns of adherence and time to stopping medication. We will assess how these measures of adherence track with patterns of alcohol use and binge drinking as reported in TLFB. GEE logistic models will be used to estimate the proportions of kudzu participants taking medication during periods of reported alcohol use and binge drinking. Concordance of adherence measures based on MEMs cap and self-report measures will be examined using weighted Kappa and correlations.

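### Aim 4 assesses tolerability of as-needed dosing only by the percentage of participants ever affected in each arm; a supportive dose-linked comparison of adverse events would add sensitivity to acute effects when events are common and dosing is infrequent

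*Combined protocol and SAP*

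**What the plan says.** Section 1.7 (Aim 4) sets out to examine tolerability under targeted, as-needed use in outpatients. Its whole AE analysis is two sentences: "Adverse clinical events (AEs) and other binary safety outcomes will be presented as percent of participants that experience the safety outcome by treatment arm", and "Binary adverse effect measures will be analyzed using exact methods, since they are expected to be uncommon". Neither contains a dosing, exposure or person-time term.

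Four other provisions bear on the point.

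- **Dosing (section 1.5.e):** "participants will be instructed to take a single 2 gram dose when they believe that drinking is imminent or anticipate a drinking session". Seven doses are supplied per week. No expected dosing frequency is given.
- **AE definition (section 1.1.c, AE Reporting):** an event counts "whether or not the event is considered medication-related".
- **Dispenser data (section 1.5.d, Measures of adherence):** "each dispenser opening is recorded as a medication event in a remote database in real time". The daily texts (section 1.1.e) also ask about medication taking. Aim 4 uses these sources for adherence and relates adherence to drinking, not to AEs.
- **As-treated analysis (section 1.7, exploratory outcomes):** dispenser openings enter as a time-dependent covariate, and their interaction with arm is estimated. No outcome is named, so AEs are neither included nor excluded.

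**The concern.** A participant who doses two or three times a week has no dose on most treatment days. AEs on those days are background in both arms and dilute an effect that follows a dose. Ever/never scoring dilutes it further: someone with one unrelated AE is already counted, and a later dose-related event cannot change that.

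Tolerability is one of the four primary objectives in section 1.2. A by-arm table with similar percentages could be read as evidence that single doses are well tolerated, when it had little chance of showing otherwise. The placebo arm takes matching capsules under the same instruction, so a blinded comparison on dosed days can largely be made from data the trial already collects.

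**Working it through.** Aim 4 states no power or detectable difference for AEs, so there is no figure to reproduce. What follows is an illustration.

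**Inputs from the documents.** 60 per arm (section 1.4: "120 participants will be randomized 1:1 to kudzu extract (2 grams) or placebo for targeted administration"); 12 weeks, or 84 days (section 1.4: "randomly assigned to receive 12 weeks of kudzu or placebo, to be taken on an as-needed basis"); percent affected, tested exactly (section 1.7, Aim 4). The two-sided 5% level is stated for other aims and is assumed here.

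**Assumed inputs.** Background 0.1 AEs per person-week, spread evenly over days; gamma frailty between participants with variance 0.5; 2.5 doses a week; AE rate doubled on dosed days in the kudzu arm only.

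**Step 1, expected AEs per participant.** Dosed fraction f = 2.5/7 = 0.357. Placebo: 0.1 × 12 = 1.2. Kudzu: 1.2 × (1 − f + 2f) = 1.2 × 1.357 = 1.63.

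**Step 2, planned analysis.** P(ever affected) = 1 − (1 + 0.5μ)^−2, where μ is the expected count from step 1.
- Placebo: 1 − 1.6^−2 = 61%. Kudzu: 1 − 1.814^−2 = 70%.
- Fisher's exact test with 60 per arm has about 12% power from these percentages, and 11% in simulated trials.

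**Step 3, counting all events on all days.**
- Expected events: 60 × 1.2 = 72 and 72 × 1.357 = 97.7. Rate ratio 1.357, log 0.305.
- SE = √(1/72 + 1/97.7 + 2 × 0.5/60) = 0.202, so z = 1.51.
- Power = Φ(1.51 − 1.96) = 33% (simulated: about 30%).

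**Step 4, counting events on dosed days.**
- Expected events: 72 × 0.357 = 25.7 and 51.4. Rate ratio 2, log 0.693.
- SE = √(1/25.7 + 1/51.4 + 2 × 0.5/60) = 0.274, so z = 2.53.
- Power = Φ(2.53 − 1.96) = 72% (simulated: 71%).

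**Step 5, misdated onsets.** If a share m of onsets is dated to a random day of the week, the dosed-day ratio falls to 2(1 − m) + 1.357m.

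| m | Ratio | Simulated power, dosed days |
|---|---|---|
| 0% | 2.00 | 71% |
| 30% | 1.81 | 61% |
| 50% | 1.68 | 47% |
| 100% | 1.36 | 31% |

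The ratio formula treats all participants as dosing equally often. The simulations let frequency vary between people.

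**Step 6, splitting the gain.** From 11% to about 30%, roughly 20 points, comes from counting events. Linkage adds 71 − 30 = 41 points with perfect dating, 47 − 30 = 17 with half misdated, and 31 − 30 = 1 with all misdated.

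**Step 7, where the result changes.** A simpler model uses no frailty and a tripled rate on dosed days. Then p(kudzu) = 1 − (1 − p0)^(1 − f + 3f), where p0 is the placebo 12-week risk.

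| p0 | Doses per week | p(kudzu) | Power, planned | Power, dosed days |
|---|---|---|---|---|
| 50% | 1 | 59% | 0.13 | 0.63 |
| 50% | 4 | 77% | 0.84 | 1.00 |
| 5% | 4 | 10% | 0.10 | 0.14 |

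The share of kudzu-arm events falling on undosed days, (1 − f)/(1 − f + 3f), is 67%, 45% and 20% at one, two and four doses a week.

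**Step 8, retention.** Section 1.7 (Aim 1) says "we conservatively estimate that 80% of participants will be retained at 12 weeks". With 120 × 0.8/2 = 48 per arm, the central case gives 9% for the planned test and 59% for dosed days.

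**The case against.** **The by-arm table answers the question asked.** Aim 4 concerns kudzu taken as needed, and undosed days belong to that strategy. The randomised comparison is valid, and the plan claims no power for AEs. This stands: the point is about sensitivity to a per-dose effect and does not show an error in the table.

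**The scenario needs common events.** The central case has 61% of placebo participants with an AE, while the plan expects adverse effects to be uncommon. The only incidence in the documents (section 1.1.b, an earlier isoflavone trial) is 1.8% against 2.0%. This stands for specific effects. With 6-11% of placebo participants affected and a doubled rate, power is 1-10% for ever/never and 0-15% for dosed days; too few events is then the limit. All-cause AEs, as section 1.1.c defines them, could be much more frequent.

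**Dating is weak.** AEs are elicited by weekly recall (section 1.1.c), Table 3 lists them at enrollment and monthly, and no onset date is mentioned. This also stands, and step 5 shows the loss. If background AEs are three times likelier on dosed days and half of onsets are misdated, the dosed-day comparison has 73% power against 65% for an all-days rate, so linkage adds little.

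**Relatedness is already judged.** A clinician gives an opinion on each AE (section 1.1.c), and AEs are reviewed weekly by possible relationship to drug. That is case-by-case judgement, and Aim 4 plans no between-arm analysis of it.

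**Dosed days are not randomised.** If kudzu changes drinking or dosing, dosed days differ between arms. This stands, and it limits the analysis to a supportive role.

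**Conclusion.** The point holds as a modest improvement. Aim 4 has no planned between-arm comparison that relates AEs to dosing, although dosing is recorded in both arms. In the central case the planned test has about 11% power. The dosed-day comparison has 47-71% with 0-50% of onsets misdated, and 31% if all are. Dosing frequency, background AE rate, frailty and effect size are all assumptions; the documents give none of them for this trial.

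Three stronger readings are tempting and not supported.

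- A reader might infer that a dose-related signal is bound to be lost among undosed days. It depends on the inputs: at four doses a week, 50% background risk and a tripled rate, the planned test has 0.84 power.
- A reader might infer that every dose is time-stamped. The stamp is on a dispenser opening, and one dose is four capsules.
- A reader might infer that the by-arm table cannot support a statement on tolerability. It can for the as-needed strategy; it is weak evidence only about acute effects of a dose.

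**What to change.** Keep the by-arm percentages and exact tests as they are, and add the following to Aim 4.

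- **Comparison:** kudzu versus placebo, AEs with onset on the day of a recorded dispenser opening or the day after. Use the daily text where dispenser data are missing.
- **Measure and model:** AEs per dosed day, from a count model with participant-level robust standard errors. State how overlapping windows are counted.
- **Contrast:** between arms only. Dosed against undosed days within an arm would be confounded by drinking.
- **Label:** supportive, because dosed days are determined after randomisation and onset comes from weekly recall.
- **Data:** confirm that the AE form records onset date, and reconcile the weekly AE schedule in section 1.1.c with the monthly entry in Table 3.

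Also state whether the exploratory as-treated analysis covers AEs.

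The cost is SAP wording and one linked analysis, plus a form change if onset date is not captured. The power figures above count only events dated to the dosed day. Including the next day brings in more background but recovers some misdated onsets, so they are a guide only.

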Official Title of the study:

A-HACK Study: Addressing Heavy Alcohol use Consumption with Kudzu

NCT number:

NCT03709043

Document Type:

Study Protocol and Statistical Analysis Plan

Date of the document:

03/12/2021

CLINICAL PROTOCOL

1.1 Overview and rationale for a pilot placebo-controlled trial and kudzu.

We propose to conduct a 12-week pilot with 1- and 3-month post-treatment follow-up, double-blind, placebo-controlled study of targeted kudzu extract among binge-drinkers with AUD at high risk for acquiring or transmitting HIV and other sexually transmitted infections (STIs). This intervention could benefit this population in two ways: reductions in binge drinking may limit harms associated with alcohol use and decrease alcohol-related sexual risk behaviors. This study will determine whether targeted oral kudzu extract (2 grams), taken on an as-needed basis, is an efficacious, tolerable and acceptable strategy among binge-drinkers who are at high risk for acquiring or transmitting HIV and other STIs. If kudzu extract is shown to be a viable strategy among binge-drinking individuals, it may ultimately expand the available interventions for this populations to reduce their alcohol consumption.

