3. Having an AUD by DSM-5 SCID criteria (includes hazardous and harmful use);
4. Interested in reducing binge alcohol consumption;
5. HIV negative by rapid antibody test or HIV positive with a medical record documentation of HIV infection*. For HIV-positive individuals, having a CD4 cell count >100 cells/mm³ and having suppressed HIV viral load with < 50 copies/mm³;
6. No current acute illnesses requiring prolonged medical care;
7. No chronic illnesses that are likely to progress clinically during trial participation;
8. Able and willing to provide informed consent and adhere to visit schedule;

9. Age 18-70 years;
10. Baseline CBC, total protein, albumin, glucose, alkaline phosphatase, creatinine, BUN, and electrolytes without clinically significant abnormalities as determined by study clinician in conjunction with symptoms, physical exam, and medical history.

***Note:** Participants newly diagnosed with HIV at screening are eligible for the study but we will postpone their enrollment until they are virally suppressed with HIV viral load < 50 copies/mm³.

1.4.e. Exclusion Criteria.

Subjects who meet *any* of the following exclusion criteria are not to be enrolled in this study:

1. Any psychiatric (e.g., depression with suicidal ideation) or medical condition that would preclude safe participation in the study;
2. Known allergy/previous adverse reaction to kudzu;
3. Moderate/severe liver disease (AST, ALT \geq 5 times upper limit of normal);
4. Impaired renal function (creatinine clearance < 50 ml/min);
5. Currently participating in another intervention research study with potential overlap;
6. Current severe substance use disorder (exclusive nicotine, cannabis and alcohol) as determined by DSM-V SCID criteria;
7. pregnant women;
8. HIV positive individuals who are not virally suppressed;
9. Any condition that, in the principal investigator and/or study clinician's judgment interferes with safe study participation or adherence to study procedures;
10. Not willing to learn how to send EMA surveys

*Eligible participants who have a partner currently in the study will be enrolled and randomized after their partner has completed their in-treatment follow-up, to reduce the concerns of contamination between treatment conditions.

1.4.f. Community input on recruitment and retention.

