This study's aim is to determine efficacy of an herbal intervention to reduce binge drinking, against a background of relatively brief counseling that would be feasible in a clinical setting with limited resources. Thus, we will adapt a manualized version of the MM brief counseling platform used in NIAAA's COMBINE study.^{150,151} In that trial, pharmacotherapy with MM showed the most significant reductions in heavy drinking days compared to 7 other treatment arms.¹⁵⁰ MM has been used in a targeted pharmacotherapy trial 98 and our team has

successfully used MM in AUD trials. MM is a low-intensity supportive program designed to increase problem recognition and enhance motivation to change maladaptive alcohol use patterns. Participants will receive individual 20 minute MM sessions weekly from trained staff supervised by a clinical psychologist.

1.1. Measures and Schedule of Data Collection Overview.

1.1.a. Medical Safety Measures.

Blood specimens will be collected for monthly safety lab assessments via venipuncture by clinicians or research associates with certified phlebotomy training. Since San Francisco is facing the COVID-19 outbreak, we will collect safety lab assessments at 6 and 12 weeks* rather than monthly until the shelter-in-place order is lifted. This is for the safety of our participants.

Table 3: Summary of Measures	Data Source	Schedule*
OUTCOME VARIABLES		
Alcohol behavioral outcomes ^{152,153}		
No. of binge drinking sessions; drinks per drinking day	TLFB ¹⁵⁴ ; SMS texts	W, D, PT
Alcohol urinary biomarker		
Urine-positivity for ethyl glucuronide (EtG) for recent alcohol use (past 3 days)	Urine Sample	E, W-6, PT
Sexually Transmitted Infections outcomes		
Incident syphilis, gonorrhea, Chlamydia, or HIV; site of infections (urethral, oral or rectal).	Biologic Samples	E, M-3, PT
Behavioral outcomes ^{152,153}		
No. of sex partners and condomless sex acts; Event-level data on alcohol and recent episodes of sex ¹⁵⁵ ; Partners on PrEP or with undetectable viral load	ACASI, S MS texts	E, M, D, PT
PrEP use and adherence / Anti-retroviral Therapy (ART) use and adherence	ACASI	E, M
Reported days / episodes of other substance use	ACASI	E, M
Alcohol treatment (outside study)	ACASI	E, M
Adherence outcomes		
Frequency and timing of pill taking	MEMs cap Dispensers	D
Self-reported adherence	ACASI; SMS texts	M; D
Safety outcomes		
Adverse events ¹⁵⁶	Self-report	E, M
Safety labs (e.g., liver enzyme levels, renal function) ¹⁵⁶	Serum Sample	E, M*

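### Section 1.7 names no analysis of the measured safety labs: Aim 4 compares only percentages with a binary event, by unspecified exact methods, which is far less sensitive to a moderate shift in liver or renal values

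*Combined protocol and SAP*

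**What the plan says.** Section 1.1 (Overview) says the trial will determine whether targeted kudzu "is an efficacious, tolerable and acceptable strategy among binge-drinkers". Section 1.2 makes tolerability and acceptability the fourth primary objective, judged by adverse clinical event rates and medication adherence.

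Table 3 (section 1.1.a, Medical Safety Measures) has a safety outcomes block containing "Safety labs (e.g., liver enzyme levels, renal function"), taken from serum at enrolment and monthly. While the shelter-in-place order lasts, "we will collect safety lab assessments at 6 and 12 weeks" instead.

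Section 1.7, Aim 4, presents adverse events and other binary safety outcomes as the percentage of participants affected in each arm, and then says: "Binary adverse effect measures will be analyzed using exact methods, since they are expected to be uncommon". It does not name the method, the error rate, a confidence interval, a tolerability criterion or a detectable effect. Aims 1 to 3 all give detectable effects.

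The AE Reporting text (section 1.1.c) is the documented route from a lab value to an event. Abnormal measures that staff consider clinically important are adverse events, worsening of a pre-existing abnormality counts, and stable pre-existing conditions do not.

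**The concern.** The liver and kidney measurements are continuous, repeated and have an enrolment value. Section 1.7 assigns them no model. If they are compared between arms only after being turned into an uncommon yes/no event, a shift in the whole distribution that pushes few people over a clinical threshold is nearly invisible.

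The enrolment value matters most for the liver. Exclusion 3 reads "Moderate/severe liver disease (AST, ALT" at five or more times the upper limit of normal), and AST and ALT are not in the laboratory list of inclusion criterion 10. Participants can therefore enter with raised enzymes, and change from enrolment is more informative than status. The same argument is weaker for the kidney, because criterion 10 covers creatinine and exclusion 4 sets a clearance limit.

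At stake is what the report can say under a primary objective. The plan as written does not tell the reader how large a lab effect, or how large an excess of events, the trial is able to exclude.

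**Working it through.** **No stated figure to reproduce.** Aim 4 has no sample size, power or detectable effect. As a check on the number per arm, the pooled two-proportion formula at 48 per arm gives detectable STI differences of 22.2 to 25.2 points for control rates of 30-40%. Aim 3 states 23-26 points, so 48 per arm is close to what the plan used.

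**Inputs from the documents**
- "Upon enrollment, 120 participants will be randomized 1:1 to kudzu extract (2 grams) or placebo" (section 1.4): 120/2 = 60 per arm.
- "we conservatively estimate that 80% of participants will be retained at 12 weeks" (section 1.7, Aim 1): 0.80 × 60 = 48 per arm.
- Two-sided 5% is stated for the efficacy aims only. It is carried over to Aim 4 here.

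**Assumptions that are not in the documents:** normal log lab values; a rise of 0.5 SD on kudzu; a control event rate of 2-10% (the plan says only that events are uncommon); Fisher's exact test; the correlations given below.

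**Binary, single threshold crossing.** The kudzu rate is p_T = 1 − Φ(z(1−p_C) − 0.5). Power comes from full enumeration of both binomials. The miss rate is 1 − power.

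| Control rate | Kudzu rate | Miss, 48 per arm | Miss, 60 per arm |
|---|---|---|---|
| 2% | 6.0% | 97.2% | 94.5% |
| 5% | 12.6% | 86.8% | 80.5% |
| 10% | 21.7% | 75.5% | 67.2% |

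The 67-97% range joins opposite corners: 60 per arm at 10%, and 48 per arm at 2%.

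**Binary, any event over three monthly draws.** The rate in each arm is 1 − P(all three correlated normal values stay below the cut-off), using the same per-draw rates.
- Least favourable corner: per-draw control rate 2%, within-person correlation 0.7, 48 per arm. The rates are 4.4% against 12.1%, and the miss rate is 86%.
- Most favourable corner: per-draw control rate 10%, correlation 0.5, 60 per arm. The rates are 21.8% against 41.5%, and the miss rate is 43%.

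**Measured values, one visit.** The test is a two-sample t-test with noncentrality d√(n/2). Baseline adjustment uses d = 0.5/√(1 − r²), which is 0.577 at r = 0.5.

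| Comparison | Noncentrality, 48 / 60 | Power, 48 / 60 | Miss, 48 / 60 |
|---|---|---|---|
| Unadjusted | 2.449 / 2.739 | 68% / 78% | 32% / 22% |
| Baseline-adjusted, r = 0.5 | 2.828 / 3.162 | 80% / 88% | 20% / 12% |

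These use a single visit, so they give the continuous analysis no credit for repeated draws.

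**Sensitivity of the single-crossing figure.** The miss rate is 55-64% at a 20% control rate and about 47-61% at 30-50%. A one-sided 5% Fisher test over 2-10% misses 54-93%. For 80% power the two-sided Fisher test needs a shift of 0.82 to 1.26 SD.

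**What zero events would show.** The two-sided 95% upper limit is 1 − 0.025^(1/n): 7.4% for 0 of 48 and 6.0% for 0 of 60.

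**The case against.** Several stronger readings are tempting, and the documents do not support them.

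- *A reader might infer that the enrolment value is ignored.* The AE definition counts worsening of a pre-existing abnormality and leaves out stable conditions, so change from entry is part of what makes an event. Events are also graded for severity and assessed for relatedness. What is lost is the size of the change below the threshold of clinical importance.
- *A reader might infer that labs are excluded from every other analysis.* Section 1.7 opens with a general statement that GEE will be used for repeated outcomes, and this could cover labs. But each aim then names its outcomes and model family, and labs appear in none. No lab analysis is named; none is ruled out.
- *A reader might infer that an upper bound is precluded.* Exact methods can include exact intervals. The interval is unspecified.
- *A reader might infer that a non-significant test will be reported as tolerability.* No text says so. Tolerability is tied to event rates and adherence, without a criterion.

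There are also fair objections of substance. This is a 120-person pilot with weekly safety review that includes lab abnormalities, and with summaries to the DSMB at least every six months. Half an SD is tied to no clinical threshold. If enzymes are often raised at entry, a 2-10% rate may be too low, and the miss rate falls to roughly 47-64% at control rates of 20-50%. A liver comparison mixes any drug effect with the benefit of drinking less. Three analytes at several visits also raise multiplicity.

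These points limit the claim and shape the fix. They do not supply an analysis of the measured values, and case-by-case monitoring does not replace an estimate by arm.

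**Conclusion.** The point holds as a gap in specification with a real cost in sensitivity. Safety outcomes that are listed and measured repeatedly have no named quantitative analysis, and the one comparison that is named is weak at this sample size.

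The size is illustrative: a miss rate of about 67-97% (single crossing) or 43-86% (any event over three draws), against 22-32% unadjusted and 12-20% baseline-adjusted at r = 0.5. It rests on normal log values, the 0.5-SD rise, the 2-10% control rate (per draw in the three-draw case), within-person correlation 0.5-0.7 in that case, and a two-sided 5% Fisher test, none of which Aim 4 states. The ordering is sturdier than the figures. Under every control rate tried, from 2% to 50%, the binary comparison missed the shift more often than the measured-value comparison at the same number per arm.

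It would go too far to say that the plan will declare kudzu tolerable on a null test, or that a particular miss rate applies to this trial. The point is a cheap improvement to how a primary objective is reported and does not invalidate the design.

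**What to change.** Add two items to Aim 4.

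1. Compare log AST, log ALT and log creatinine at the on-treatment visits between arms in a linear mixed model with arm, visit and the enrolment value. Report kudzu/placebo ratios with 95% confidence intervals, labelled as supportive estimates with no multiplicity claim. Section 1.7 already uses linear mixed models for its exploratory outcomes, so the method is not new to the plan.
2. For binary safety outcomes, report the exact 95% confidence interval for the risk difference beside the planned percentages, and word the tolerability statement by the excess that the interval excludes.

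The cost is a few sentences and a little programming on data already collected, with no new visits, samples or participants. The downsides are a few more estimates, a tolerability statement that may be less favourable, and a liver ratio that must be described as the net effect of the drug and of any reduction in drinking.
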